5.9 EKG

5.10 Blood Tumor Markers

Serum tumor markers such as CA 27-29, CEA and CA-125 may be measured at the discretion of the investigator as a supplement to clinical parameters for monitoring of response.

5.11 Archival Tumor Tissue Collection

Archival tumor tissue will be collected for Exploratory Studies (see Section 8). This tissue from a prior biopsy or surgery will also be collected for routine analysis if confirmation of diagnosis or histologic subtype is uncertain from available data.

5.12 Tumor Assessments

Tumor assessments will be conducted according to protocol timeline at 9 week intervals, with CT, MRI or other appropriate imaging, as well as physical exam and clinical measurements as appropriate while on study drug during Year 1. Tumor imaging will be obtained every 12 weeks after drug discontinuation, per standard of care, or during Year 2 of study treatment. RECIST version 1.1 will be used in this study for assessment of tumor response. While either CT or MRI may be utilized, as per RECIST 1.1, CT is the preferred imaging technique in this study.

Bone scans will be performed at screening for any subject with known bone metastases and/or new bone pain and musculoskeletal complaints. During the study, bone scans will be performed as needed for evaluation of worsening and/or new bone pain and musculoskeletal complaints or if the site believes they have attained a Complete Response. If a subject has no known metastatic disease in the bone or active symptoms, a bone scan at baseline is not needed. A bone scan can be obtained at follow up if there are new symptoms of bone pain.

5.13 Adverse Event Assessment

Adverse event assessment will be undertaken at every clinical visit. See 5.14.

An investigator who is a qualified physician will evaluate all adverse events according to the NCI Common Terminology for Adverse Events (CTCAE), version 4.0. Any adverse event which changes CTCAE grade over the course of a given episode will have each change of grade recorded on the adverse event case report forms/worksheets.

All adverse events regardless of CTCAE grade must also be evaluated for seriousness.

5.14 Concomitant Medications

Concomitant Medications will be assessed at every clinical visit. See 5.14.

5.15 Time and Events Table

	Screening				End of Treatment ⁴	SOC Follow- up ⁵								
Procedure	(Within 6 weeks of Day 1)	C1 D1	C1 D8	C1 D15	C2 D1	C2 D8	C3 D1	C4 D1	C5 D1	C6 D1	Even Cycles	Odd Cycles	30-days after drug discontinuation, +/- 7 days	Every 12 Weeks
Informed Consent ¹	Х													
Tempus HRD ¹¹	Х													
Physical Exam (includes Medical history)	х	х	х	х	х		х	х	х	х	X	×	Х	Х
Vitals ²	Х	Х	Х	Х	Х		Х	Х	Х	Х	Х	Х	Х	Х
ECOG Performance Status	х	х			Х		Х	Х	Х	Х	Х	Х	Х	Х
Hematology ⁸	Х	Х	Х	Х	Х	Х	Х	Х	Х	Х	Х	Х	Х	Х
Chemistry ⁸	Х	Х	Х	Х	Х	Х	Х	Х	Х	Х	Х	Х	Х	Х
Tumor markers (CA2729, CEA, CA- 125)		as per standard of care, at the investigator's discretion												
T3 Free, T4 Free, TSH ⁸	Х				Х			Х		Х	Х		Х	
Coagulation (PT, INR, aPTT)	X ⁸													
Urine or serum pregnancy test	X ₈													
EKG	Х													
Archival Tumor Tissue Collection	X ¹⁰													
CT Scan (Chest, Abdomen, Pelvis) and/or MRI	×		As clinically indicated (or every 9 weeks for Response assessment)						Х					
Whole body Bone Scan	Х		As clinically indicated											

Procedure	Screening (Within 6 weeks of Day 1)	Treatment Phase (+/- 3 days) ³											End of Treatment ⁴	SOC Follow- up ⁵
		C1 D1	C1 D8	C1 D15	C2 D1	C2 D8	C3 D1	C4 D1	C5 D1	C6 D1	Even Cycles	Odd Cycles	30-days after drug discontinuation, +/- 7 days	Every 12 Weeks
Adverse Event Assessment	Х		Х	Х	X		Х	Х	Х	Х	х	Х	Xe	X ⁶
Concomitant Medications	Х		Х	Х	X		Х	Х	Х	Х	Х	Х	Х	Х
Pembrolizu mab Administrati on		x			х		х	х	х	Х	Х	Х		
Olaparib Administrati on and Olaparib Compliance Diary			Daily ⁷											

¹Informed consent may be obtained within 6 weeks of Cycle 1, Day 1

²Vital signs to include temperature, pulse, respiratory rate, weight, and blood pressure. Height will be measured at Screening only.

³Study treatment is up to 35 administrations of pembrolizumab (approximately two years).

⁴If subject discontinues drug due to progression, the End of Treatment visit (30 days after study treatment discontinuation, +/- 7 days) will end their participation in the study and will not be followed thereafter.

⁵Subjects who discontinue trial treatment for a reason other than disease progression will move into the Follow-Up Phase and should be assessed every 12 weeks (56 ± 7 days) by radiologic imaging to monitor disease status, per standard of care for up to two years of total study participation.

⁶SAEs and ECIs should be reported for 90 days after last pembrolizumab dose or until new anticancer treatment is initiated, but for a minimum of 30 days, whichever occurs first.

⁷Olaparib will be dispensed each cycle day 1 (each cycle=3 weeks). Subjects will be given an olaparib dosing diary at Cycle 1 Day 1, and at Day 1 of each subsequent cycle while taking olaparib. The completed diary will be collected at the next cycle Day 1. Olaparib dosing must begin within 3 days of pembrolizumab C1D1.

⁸Laboratory tests for screening should be performed within 10 days prior to the first dose of pembrolizumab. After Cycle 1, pre-dose laboratory procedures can be conducted up to 72 hours prior to dosing. Results must be reviewed by the investigator or qualified designee and found to be acceptable prior to each dose of trial treatment.

⁹ Female subjects of childbearing potential should have a negative urine or serum pregnancy prior to study registration and re-tested within 72 hours prior to receiving the first dose of pembrolizumab. If the urine test is positive or cannot be confirmed as negative, a serum pregnancy test will be required.

¹⁰The pre-treatment archival tumor tissue sample for correlative studies may be sent to QualTek any time after eligibility verification.

¹¹ Tempus testing will be performed only on patients who do not otherwise qualify based on BRCA status. Archival tumor tissue plus a normal matching sample (blood preferred) will be collected and shipped to Tempus. De-identified clinical data elements will be shared with Tempus as specified in the master

agreement (may be sent after screening).

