4.6 Duration of Follow Up

Primary and secondary response objectives will be met with approximately 1 month end of study follow-up for subjects discontinuing therapy due to progression. Subjects who discontinue trial treatment for a reason other than disease progression will move into the Follow-Up Phase and should be assessed every 12 weeks (56 ± 7 days) by radiologic imaging to monitor disease status, per standard of care for up to two years of total study participation. Every effort should be made to collect information regarding disease status until the start of new anti-neoplastic therapy, disease progression, death, or at end of the study.

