6.2 Steps to Determine If an Adverse Event Requires Expedited Reporting

- Step 1: Identify the type of adverse event using the NCI Common Terminology Criteria for Adverse Events (CTCAE v4).
- Step 2: Grade the adverse event using the NCI CTCAE v4.

Step 3: Determine whether the adverse event is related to the protocol therapy Attribution categories are as follows:

- Definite The AE *is clearly related* to the study treatment.
- Probable The AE is likely related to the study treatment.
- Possible The AE *may be related* to the study treatment.
- Unrelated The AE is clearly NOT related to the study treatment.

Note: This includes all events that occur within 30 days of the last dose of protocol treatment. Any event that occurs more than 30 days after the last dose of treatment and is attributed (possibly, probably, or definitely) to the agent(s) must also be reported accordingly. SAEs and ECIs should be reported for 90 days after last pembrolizumab dose or until new anticancer treatment is initiated, but for a minimum of 30 days, whichever occurs first.

Step 4: Determine the prior experience of the adverse event.

Expected events are those that have been previously identified as resulting from administration of the agent. An adverse event is considered unexpected, for expedited reporting purposes only, when either the type of event or the severity of the event is not listed in the current known adverse events listed in:

- the current known adverse events listed this protocol;
- the drug package insert; and/or
- the current Investigator's Brochure

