- There is a satisfactory explanation other than the study drug for the changes observed; or
- Death.

Serious adverse events, occurring after the informed consent is signed but prior to the initial dose of the investigational product will be collected as part of the subject's medical history/baseline symptoms but will only be reportable if they are considered by the Investigator to be causally related to required research procedures.

SAEs and ECIs should be reported for 90 days after last pembrolizumab dose or until new anticancer treatment is initiated, but for a minimum of 30 days, whichever occurs first.

If a laboratory abnormality is one component of a diagnosis or syndrome, then only the diagnosis or syndrome should be recorded on the AE page/screen of the eCRF. If the abnormality was not a part of a diagnosis or syndrome, then the laboratory abnormality should be recorded as the AE.

¹ An abnormal laboratory value is considered to be an AE if the abnormality: 1) results in discontinuation from the study; 2) requires treatment, modification/ interruption of IP dose, or any other therapeutic intervention; or 3) is judged to be of significant clinical importance. Regardless of severity grade, only laboratory abnormalities that fulfill a seriousness criterion need to be documented as a serious adverse event.

Non-serious adverse events (AEs) will be collected throughout the treatment period through the End of Treatment assessment 30 days after removal from treatment. Patients removed from treatment for unacceptable adverse events will be followed until resolution or stabilization of the adverse event. Events occurring during this period must be followed until resolution or death unless in the Investigator's opinion, the condition is unlikely to resolve due to the patient's underlying disease. After the End of Treatment assessment, any adverse event documented in the subject's medical record as being at least possibly related to study intervention will also be recorded in the Case Report Form.

SAEs must be reported to oversight agencies as described below.

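### The ±7-day window lets the End of Treatment visit fall from day 23, so scheduled adverse-event ascertainment can stop up to 7 days short of the 30 days that Sections 6.2, 6.3 and 6.4.1 name

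*Combined protocol and SAP*

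**What the plan says.** - **Section 5.15, column header and footnote 4.** The End of Treatment visit is set at 30 days after discontinuation, with a tolerance of 7 days either way. For subjects who stop for progression, "the End of Treatment visit (30 days after study treatment discontinuation, +/- 7 days) will end their participation in the study", and they are not followed after it.
- **Section 4.6.** "Subjects who discontinue trial treatment for a reason other than disease progression will move into the Follow-Up Phase", with imaging every 12 weeks. In the table, the AE mark in that follow-up column carries footnote 6, which concerns only SAEs and ECIs.
- **Section 6.3.** "Non-serious adverse events (AEs) will be collected throughout the treatment period through the End of Treatment assessment 30 days after removal from treatment". No tolerance is given. After that assessment, the case report form takes AEs that the medical record documents as at least possibly related.
- **Section 6.2.** On expedited reporting: "This includes all events that occur within 30 days of the last dose of protocol treatment". Later events are reportable too when they are judged at least possibly due to the study drugs.
- **Section 6.4.1.** The principal investigator is to be told of SAEs that occur on study or within 30 days of the last administration of study drug.
- **Footnote 6 of Section 5.15** (repeated in Sections 6.2, 6.3 and 6.4.1). SAE and ECI reporting runs for 90 days after the last pembrolizumab dose or until new anticancer treatment, "but for a minimum of 30 days, whichever occurs first".

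**The concern.** Section 6.3 treats the End of Treatment assessment and day 30 as the same point. The window in Section 5.15 allows them to differ by a week in either direction. A visit before day 30 is on schedule, yet it ends routine collection of non-serious AEs before the period that Section 6.3 names. For a subject who stops for progression it is also the last contact the protocol plans.

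Two things are at stake. Some post-treatment events will not be looked for in part of a period that the protocol says it covers. The length of that period will also differ between subjects for reasons of scheduling alone. With 20 subjects, a few missed events can be visible in a safety table.

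**Working it through.** **Inputs**

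| Item | Value | Source |
|---|---|---|
| End of Treatment visit | 30 ± 7 days after discontinuation | 5.15 header, footnote 4 |
| Non-serious AE collection | to that visit, placed 30 days after removal | 6.3 |
| Events covered | 30 days from last dose of protocol treatment | 6.2 |
| SAE notification | 30 days from last administration of study drug | 6.4.1 |
| SAE/ECI reporting | 90 days from last pembrolizumab dose, 30-day minimum | footnote 6 |
| Pembrolizumab | every 3 weeks | 4.1 |
| Olaparib | twice daily, continuous | 4.1, Table 2 |

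**1. The plan's own window.** Earliest visit 30 − 7 = day 23; latest 30 + 7 = day 37.

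**2. Shortfall counted from discontinuation (Section 6.3).** Shortfall = max(0, 30 − visit day).
- Day 23: 30 − 23 = 7 days, or 7/30 = 23% of the period (days 24 to 30).
- Days 30 to 37: 0.
- If visits were spread evenly over the 14-day span (an assumption; the documents give no distribution), half would fall before day 30. The mean shortfall would be 7/2 = 3.5 days among those, or 1.75 days over all subjects.

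**3. Shortfall counted from the last dose (Sections 6.2, 6.4.1, footnote 6).** Let g be the days from the relevant last dose to discontinuation. For a day-23 visit, shortfall = max(0, 30 − 23 − g).

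| g (days) | Day-23 visit, counted from last dose | Shortfall against 30 days |
|---|---|---|
| 0 | 23 | 7 |
| 3 | 26 | 4 |
| 7 | 30 | 0 |
| 14 | 37 | 0 |
| 21 | 44 | 0 |

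Sections 6.2 and 6.4.1 count from the last dose of protocol treatment or study drug. Olaparib is taken daily, so g can be at or near 0 and the shortfall can be the full 7 days. It is smaller if olaparib was already interrupted. Footnote 6 counts from the last pembrolizumab dose, for which g may be anything from 0 to 21 days if no dose was delayed (an assumption). Its 30-day minimum is missed only if g is below 7.

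**4. Which events are affected on days 24 to 30 after a day-23 visit.**

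| Event | Still reportable by text? | Planned contact for progression subjects? |
|---|---|---|
| Non-serious, unrelated | No | No |
| Non-serious, at least possibly related | Yes, if in the medical record (6.3) | No |
| SAE or ECI | Yes (6.2, 6.4.1, footnote 6) | No |

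The first row applies to subjects who stop for other reasons as well, because Section 6.3 ends routine non-serious collection at the visit for everyone and the follow-up AE mark is limited by footnote 6.

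**5. After a -0/+7 window.** Visits fall on days 30 to 37, and the shortfall against 30 days is 0. Against the 90-day SAE/ECI period, with g = 0, 90 − 37 = 53 to 90 − 30 = 60 days still lie after the visit that ends participation. Under the present window the range is 53 to 90 − 23 = 67.

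**The case against.** A symmetric visit window is ordinary, and this one was added deliberately in Version 6. Section 6.3 defines the end of non-serious collection as the visit itself and never calls 30 days a minimum. Section 4.6 speaks of roughly one month of follow-up, which fits reading 30 days as a nominal time. On that reading there is little conflict inside Section 6.3. This has weight, but it does not reach the last-dose periods in Sections 6.2 and 6.4.1, which are stated as 30 days and are not tied to a visit.

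A reader might infer something stronger: that the visit closes all AE collection, that the window breaks every 30-day rule for every subject, and that the 23-to-37-day spread biases the safety results. The documents do not support this.
- Participation ends at the visit only for subjects who stop for progression.
- Related AEs, SAEs and ECIs remain reportable afterwards by explicit text.
- Section 6.3 also follows subjects removed for unacceptable AEs until resolution or stabilization.
- The 30 days in footnote 6 is a floor for SAEs and ECIs within a 90-day period, and it is often already past when pembrolizumab was last given a week or more before discontinuation.
- Section 9 plans no post-treatment AE rate and no comparison that unequal follow-up could distort.

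It is also fair to say that the window is the smaller of two problems. Ending participation by day 37 does not fit a 90-day SAE/ECI period whatever the window, and editing the window does not cure that. What remains is still a real mismatch with a cheap remedy.

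**Conclusion.** The point holds in a limited form and is minor. A compliant End of Treatment visit on days 23 to 29 ends scheduled AE ascertainment up to 7 days before the 30 days named in Section 6.3. It does the same for Sections 6.2 and 6.4.1 when the last olaparib dose is at or near discontinuation. For footnote 6 the breach is conditional: it needs a last pembrolizumab dose fewer than 7 days before discontinuation.

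The definite loss is non-serious, unrelated AEs that start on days 24 to 30. To this is added the loss of scheduled detection of other events in subjects who stop for progression: such events must be reported, but nothing is planned to find them.

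The conclusion takes removal from treatment (Section 6.3) and discontinuation (footnote 4) to be the same date. How many subjects would be seen early cannot be told from the documents.

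**What to change.** Change the End of Treatment window in the Section 5.15 column header and in footnote 4 to 30 days, -0/+7 days. This brings the shortfall counted from discontinuation to zero. Because the last dose cannot come after discontinuation, it does so for the last-dose periods too. The cost is two text edits and some visits up to a week later; no visit is added and no treatment rule changes. If post-treatment AEs are tabulated, count them to day 30 for every subject so that the period is equal.

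In the same amendment, reconcile footnotes 4 and 6 with Sections 6.2, 6.3 and 6.4.1:
- use one start date, since the passages now count variously from discontinuation, removal, last dose of any study drug and last pembrolizumab dose;
- state how SAEs and ECIs will be ascertained up to 90 days after the last pembrolizumab dose in subjects whose participation has ended at the visit. A telephone call or record review would be one way, at the cost of a contact per subject.

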2.2 Secondary Objectives

- **2.2.1** Progression Free Survival (PFS), as measured by RECIST 1.1, in patients progressing after prior therapy from baseline to the date of the first evidence of progression for up to two years.
- **2.2.2** Overall survival (OS), from baseline until death for up to two years.
- **2.2.3** Clinical Benefit Rate (CR+PR+SD), as measured by RECIST 1.1, in patients progressing after prior therapy from baseline for up to two years.
- **2.2.4** Duration of Response (DOR) for CR and PR, as measured by RECIST 1.1, in patients progressing after prior therapy from baseline for up to two years.

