4.5 Duration of Therapy

Patients will continue with pembrolizumab until disease progression or unacceptable toxicity, or until completion of 35 treatments of pembrolizumab (approximately 2 years), as long as in the Investigator's opinion they are benefiting from treatment and they do not meet any other discontinuation criteria. Once patients have been discontinued from study treatment, other treatment options (including compassionate use) will be at the discretion of the investigator. Subjects will receive olaparib according to the FDA approved package insert until disease progression or unacceptable toxicity.

In patients with initial disease progression substantiated by radiographic imaging per RECIST 1.1, study treatment may continue until repeat imaging is conducted, at least 4 weeks and no later than 8 weeks later, under the following conditions:

- No worsening of ECOG Performance Status
- No clinically relevant increases in disease-related symptoms thought to be associated with disease progression
- No requirement for intensified management of disease-related symptoms exists, including increased analgesia, radiotherapy, or other palliative care.

Disease progression can also be confirmed histologically, cytologically, or surgically, or by physical examination or other clinical signs, per PI discretion.

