6.1.4 Serious Adverse Events

A "serious" adverse event is defined in regulatory terminology as any untoward medical occurrence that:

· Results in death.

If death results from (progression of) the disease, the disease should be reported as event (SAE) itself.

Is life-threatening.

(the patient was at risk of death at the time of the event; it does not refer to an event that hypothetically might have caused death if it were more severe).

- Requires in-patient hospitalization or prolongation of existing hospitalization for ≥ 24 hours.
- Results in persistent or significant disability or incapacity.
- Is a congenital anomaly/birth defect
- Is an important medical event

Any event that does not meet the above criteria, but that in the judgment of the investigator jeopardizes the patient, may be considered for reporting as a serious adverse event. The event may require medical or surgical intervention to prevent one of the outcomes listed in the definition of "Serious Adverse Event".

For example: allergic bronchospasm requiring intensive treatment in an emergency room or at home; convulsions that may not result in hospitalization; development of drug abuse or drug dependency.

Pregnancy: If a female subject or male subject's female partner inadvertently becomes pregnant while on treatment with pembrolizumab, the subject will immediately be removed from the study. The site will contact the subject at least monthly and document the subject's status until the pregnancy has been

completed or terminated. The outcome of the pregnancy will be reported to the IRB and to Merck within 10 days of the PI becoming aware of the outcome. If the outcome is a serious adverse experience (e.g., death, abortion, congenital anomaly, or other disabling or life-threatening complication to the mother or newborn), the PI upon learning of the event, will report to Merck.

The study investigator will make every effort to obtain permission to follow the outcome of the pregnancy and report the condition of the fetus or newborn to the IRB.

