6.3 Data Collection Procedures for Adverse Events

The principal investigator is responsible for evaluating all adverse events, obtaining supporting documents, and determining that documentation of the event is adequate. He/she is responsible for determining the seriousness, severity, and relationship of the adverse event to the investigational drug. The principal investigator may delegate these duties to sub-investigators and must assure that these sub-investigators are qualified to perform these duties under the supervision of the principal investigator. All adverse events will be documented in the subject's source and recorded on Case Report Form(s).

The term of the adverse event should reflect the diagnosis rather than its symptoms, when available. In the event of death, the cause of death should be recorded as the adverse

IIT2015-18-[name]-MK3475

event. The detailed description of the event will include appropriately graded severity of the adverse event and its relationship to the study drug.

"Lack of efficacy" or "failure of expected pharmacological action" per se will not be reported as an AE or SAE. However, the signs and symptoms and/or clinical sequelae resulting from lack of efficacy will be reported if they fulfill the definition of an AE or SAE.

Events that **do not** meet the definition of an AE include:

Any clinically significant abnormal laboratory finding or other abnormal safety assessments that is associated with the underlying disease, unless judged by the investigator to be more severe than expected for the subject's condition.

Abnormal laboratory findings deemed by the investigator as not clinically significant.

The disease/disorder being studied, or expected progression, signs, or symptoms of the disease/disorder being studied, unless more severe than expected for the subject's condition

Medical or surgical procedure (e.g., endoscopy, appendectomy); the condition that leads to the procedure is an AE

Situations where an untoward medical occurrence did not occur (social and/or convenience admission to a hospital)

Anticipated day-to-day fluctuations of pre-existing disease(s) or condition(s) present or detected at the start of the study that do not worsen

All patients experiencing an adverse event will be monitored until:

- The adverse event resolves or the symptoms or signs that constitute the adverse event return to baseline:
- Any abnormal laboratory values have returned to baseline¹;

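### Overall survival is a two-year secondary objective, but no vital-status follow-up is planned after progression, so the Kaplan-Meier estimate would in practice censor patients because they progressed

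*Combined protocol and SAP*

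**What the plan says.** Section 2.2.2 lists "Overall survival (OS), from baseline until death for up to two years". Section 9.3.2 says time-to-event outcomes will be estimated by the Kaplan-Meier method. It gives no censoring rule for OS.

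For patients who stop because of progression, footnote 4 of the Time and Events Table (5.15) says the End of Treatment visit, 30 days (± 7) after discontinuation, "will end their participation in the study and will not be followed thereafter". Section 4.6 agrees and gives the reason: "Primary and secondary response objectives will be met with approximately 1 month end of study follow-up for subjects discontinuing therapy due to progression". OS is not a response objective and is not mentioned there.

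Patients who stop for another reason enter a Follow-Up Phase with 12-weekly assessments for up to two years of total participation. For them, section 4.6 asks for every effort to "collect information regarding disease status until the start of new anti-neoplastic therapy, disease progression, death, or at end of the study".

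Two provisions extend observation somewhat. Section 4.5 allows that after a first RECIST progression "study treatment may continue until repeat imaging is conducted, at least 4 weeks and no later than 8 weeks later", under stated conditions. Section 6.2 (repeated in 6.3, 6.4.1 and footnote 6 of 5.15) says "SAEs and ECIs should be reported for 90 days after last pembrolizumab dose or until new anticancer treatment is initiated", with a 30-day minimum.

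**The concern.** An OS curve to two years needs to know, for each patient, whether and when death occurred, whatever happened to the tumour first. Here the event that ends follow-up is progression, which usually precedes death in advanced breast cancer. Kaplan-Meier treats a censored patient as having the same future risk as those still under observation. If patients leave observation because they progressed, those who remain are mostly progression-free, and the curve reflects their risk rather than the cohort's.

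A secondary result would then be reported that was not measured to its stated horizon and is probably too favourable. Deaths that were never recorded cannot be recovered by analysis.

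**Working it through.** **1. The passages side by side**

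| Group | Planned observation | Vital status to 24 months? |
|---|---|---|
| Stops for progression | About 30 days, then participation ends (4.6; 5.15 footnote 4) | No |
| Stops for another reason | 12-weekly visits; disease-status collection until progression, new therapy, death or study end (4.6; 5.15 footnote 5) | Largely, until progression or new therapy |
| Either group, safety reporting | Generally 90 days after last pembrolizumab dose or until new anticancer treatment; some events longer (6.2, 6.3) | Selective |

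Section 4.7 says removed patients are followed up per protocol, which leads back to these rules.

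Whether safety reporting would catch a death from the cancer is itself unclear. Section 6.1.4 says "If death results from (progression of) the disease, the disease should be reported as event (SAE) itself". Section 6.3 lists among things that are not adverse events "The disease/disorder being studied, or expected progression, signs, or symptoms of the disease/disorder being studied", unless more severe than expected. These two need reconciling.

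**2. Illustration of the effect**

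The documents give no OS figure to reproduce, so the size can only be illustrated. Inputs:

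- Median time to first event (progression or death) 6 months. Section 1.1 cites this as median PFS for PARP inhibitors; using it here is an assumption.
- Fraction of first events that are deaths, f = 0.10: assumed.
- Median survival after progression 12 months: assumed.
- Exponential times, treatment stopping at progression, 24 months of potential follow-up for everyone, all deaths captured until c months after progression and none later: assumed. c = 1 reflects footnote 4; c = 3 reflects the 90-day window.

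Hazards per month: first event λ = ln 2/6 = 0.1155; death before progression fλ = 0.01155; death after progression μ = ln 2/12 = 0.05776.

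True 24-month OS:
S = e^(−24λ) + [(1−f)λ/(λ−μ)] × (e^(−24μ) − e^(−24λ)) = 0.0625 + 1.8 × (0.25 − 0.0625) = 0.40.

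What Kaplan-Meier estimates: once t exceeds c, the ratio of progressed patients still observed to progression-free patients is r = 1.8 × (e^((λ−μ)c) − 1), and the observed death hazard is h = (fλ + μr)/(1 + r). Before time c, the same formulas apply with t in place of c.

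- c = 1: r = 0.107, h = 0.01602. Cumulative hazard = 0.0138 (month 1) + 23 × 0.01602 = 0.382. Estimate = e^(−0.382) = 0.68.
- c = 3: r = 0.341, h = 0.02329. Cumulative hazard = 0.0535 (months 1 to 3) + 21 × 0.02329 = 0.543. Estimate = e^(−0.543) = 0.58.

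Of the 60% who die within 24 months, about 23% (c = 1) or 38% (c = 3) would be recorded. A separate simulation gives the same values within rounding.

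**3. What drives the direction**

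The post- to pre-progression death hazard ratio is μ/(fλ), that is, median PFS divided by (f × post-progression median). Centrally it is 6/(0.10 × 12) = 5. If it were 1, h would equal fλ throughout and there would be no bias.

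Over 27 combinations (PFS 4, 6, 9 months; f 5, 10, 20%; post-progression median 6, 12, 18 months) the ratio runs from 4/(0.20 × 18) = 1.1 to 9/(0.05 × 6) = 30. The overstatement runs from about 2 to 45 points (c = 1) and 1.5 to 25 points (c = 3).

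**The case against.** **Safety reporting captures later deaths.** This partly stands. Adding the 8-week allowance in 4.5 to the 90-day window gives 56 + 90 = 146 days, or 146/30.44 = 4.8 months, and a reader might infer that nothing is recorded beyond that. The documents do not support such a ceiling. Section 6.2 requires reporting of attributed events more than 30 days after the last dose. Section 6.3 follows events arising on treatment or within 30 days until resolution or death, with an exception for underlying disease, and records later possibly related events found in the medical record. None has an end date. But these routes depend on attribution or an ongoing event, so they are not survival follow-up of the cohort.

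**Patients who stop for other reasons are followed properly.** Largely so, until progression or new therapy. Their 12-weekly schedule includes examination, ECOG status, laboratory tests and adverse events, so it would be wrong to say that only scans are collected. The gap lies essentially after progression.

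**No censoring rule is stated, so no faulty one is planned.** True. Censoring at last contact is an inference, but it is what Kaplan-Meier analysis does by default when follow-up ends.

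**The calculation assumes its own direction.** Correct. Every scenario sets a higher death hazard after progression than before. The results illustrate the mechanism; they are not independent evidence for it.

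**Conclusion.** The point stands: followed as written, the plan cannot deliver OS as section 2.2.2 defines it. That conclusion rests on the text alone.

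The upward bias is conditional on a higher death hazard after progression than before it, which is plausible but not quantified in the documents. A reader might take the 28- and 18-point gaps (68 − 40 and 58 − 40) as the expected error. They follow from assumed values for deaths without progression and for post-progression survival, and should not be quoted as an estimate.

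A reader might also infer that hardly anyone would be at risk at 24 months. That depends heavily on closing at month 42, which the Study Summary gives only as an estimate, so no such figure is relied on here.

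Nor does this threaten the trial's main conclusion. ORR, PFS and the two-stage rule on clinical benefit do not use post-progression survival. OS is a secondary, uncontrolled endpoint in a 20-patient pilot with no decision attached. The change is worth making because it is cheap and the missing deaths cannot be restored afterwards.

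**What to change.** Amend footnote 4 of 5.15 and section 4.6 so that vital status is recorded by chart review or telephone about every 12 weeks for all treated patients, whatever the reason for stopping and regardless of new therapy. Continue until death, withdrawal of consent, 24 months from baseline or study close, whichever comes first. No extra visits or scans are needed. Add to 9.3.2 that patients not known to have died are censored at the date last known alive.

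If survival follow-up is not wanted, delete OS from 2.2.

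Cost of the first option: at most about eight checks per patient (24 months is about 104 weeks, and 104/12 = 8.7) for about 20 patients, plus consent wording for survival contact. Either option needs a written amendment with IRB approval (10.8), so deletion is not free either.
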